### **Serious Adverse Events**

Serious adverse event collection begins after the patient or surrogate has signed informed consent. If a patient experiences a serious adverse event after consent, but prior to protocol initiation, the event will NOT be collected unless the investigator feels the event may have been caused by a protocol procedure.

Study site personnel must alert the principal investigator or his designee of any **serious and study procedure related** adverse event within 24 hours of investigator awareness of the event.

A serious adverse event is any adverse event that results in one of the following outcomes and is not classified as a clinical outcome of ARDS using the definitions noted above:

- Death that is not related to ARDS or a sequela of ARDS or death that is considered by the investigator to be related to study procedures
- A life-threatening experience (that is, immediate risk of dying)
- Persistent or significant disability/incapacity

Important medical events that may not result in death or be life-threatening may be considered serious adverse events when, based upon appropriate medical judgment, they may jeopardize the patient and may require medical or surgical intervention.

### **Data Safety Monitoring Board**

This study will use a DSMB to regularly monitor data from this trial, review and assess the performance of its operations, and make recommendations. Three members of the Division of Pulmonary and Critical Care Medicine, Division of Acute Care Surgery and/or Division of Emergency Critical Care who are not involved in this project will independently review this study on a semi-annual basis.

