## 4 Study Population and Enrollment

### 4.1 Number/Source/Screening

The trial will accrue 20 patients over a 1 to 2 year interval. Patients will be recruited from the emergency departments and the critical care medicine unit (CCMU). The overall strategy is to screen and enroll early, every newly intubated, acutely ill medical patient, using clinically obtained blood gases.

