### **9.3 Risk of Death**

It is unlikely that one treatment arm may lead to more deaths; mortality will be monitored during the course of the 24-hour study, but is not a clinical outcome of this trial.

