### **9.4 Minimization of Risks**

Federal regulations at 45 CFR 46.111(a)(1) require that risks to subjects are minimized by using procedures which are consistent with sound research design. Oxygen saturations and arterial blood gases, if indicated, will be monitored during the mini-BAL procedures. We will use a high PEEP protocol based on those used in multiple large clinical trials, that were shown safe, feasible, and of potential clinical benefit for the intended population or moderate to severe ARDS. The DSMB will be reviewing data as outlined above and will examine not only efficacy but safety (inclusive of mortality) and will reserve the right to halt the study at any time.

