# **11 Adverse Events**

Assuring patient safety is an essential component of this protocol. Each participating investigator has primary responsibility for the safety of the individual participants under his or her care. The Investigators will determine daily if any clinical adverse experiences occur during the period from enrollment through the end of the protocol, 24 hours after enrollment.

The following adverse events will be collected in the adverse event case report forms:

- Serious adverse events
- Non-serious adverse events that are considered by the investigator to be related to study procedures

- Adverse events that lead to permanent discontinuation of the study procedures

A clinical trial adverse event is any untoward medical event associated with the use of a drug or study procedure in humans, whether or not it is considered related to a drug or study procedure.

If a patient's treatment is discontinued as a result of an adverse event, study site personnel must report the circumstances and data leading to discontinuation of treatment in the adverse event case report forms.

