### **Clinical Outcomes**

Routine clinical outcomes of ARDS are exempt from adverse event reporting unless the investigator deems the event to be related to the conduct of study procedures. The following are examples of events that will be considered clinical outcomes:

- Death related to ARDS or a sequela of ARDS based on the interpretation of the investigator.
- Cardiovascular events: the need for vasoactive drugs or fluids for hypotension or hypotension.
- Respiratory events: decreased  $\text{PaO}_2/\text{FiO}_2$ , hypoxia, worsening acute respiratory distress syndrome, or respiratory failure, unless related to performance of the mini-BALs.
- Hepatic events: hepatic injury or liver dysfunction that leads to an increase from baseline in the serum level of bilirubin.
- Renal events: renal failure, renal insufficiency, or renal injury that leads to an increase from baseline in serum creatinine.
- Hematologic/coagulation events: coagulopathy, disseminated intravascular coagulation, thrombocytopenia, or thrombocytosis.
- Systemic inflammatory response syndrome related criteria: tachypnea, tachypnea, leukocytosis, leukopenia, hypothermia, hyperthermia, tachycardia, or bradycardia that does not meet the definition of severe and prolonged.

Note: Arrhythmias such as atrial fibrillation, heart block, ventricular tachycardia or ventricular fibrillation are not considered clinical outcomes and should be recorded as adverse events if they are serious events, are considered by the investigator to be related to study protocol, or lead to discontinuation of the protocol.

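### The DSMB meets by calendar only, has no written route for serious related events between meetings, and is asked to review mortality that is collected for 24 hours only

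*Combined protocol and SAP*

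**What the plan says.** **Timing of review.** Section 11 (Data Safety Monitoring Board) names three members not involved in the project who "will independently review this study on a semi-annual basis". Section 4.1 gives the accrual: "The trial will accrue 20 patients over a 1 to 2 year interval". No review is tied to a patient count or an event, and no stopping boundary is given.

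**Remit.** Section 9.4 states: "The DSMB will be reviewing data as outlined above and will examine not only efficacy but safety (inclusive of mortality", and adds that the board "will reserve the right to halt the study at any time". No section before 9.4 lists data that go to the board. The nearest candidates are Section 6.3 (study assessments) and Section 9.3 (deaths), and neither mentions it.

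**Event reporting.** Under Serious Adverse Events, "Study site personnel must alert the principal investigator or his designee of any" serious, procedure-related event within 24 hours of awareness. The text does not say who informs the DSMB, or when.

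**Mortality and the collection window.** Section 9.3: "mortality will be monitored during the course of the 24-hour study, but is not a clinical outcome of this trial". Section 11 collects adverse events "during the period from enrollment through the end of the protocol, 24 hours after enrollment". The Clinical Outcomes list includes "Death related to ARDS or a sequela of ARDS based on the interpretation of the investigator", and events on that list are exempt from adverse-event reporting unless the investigator judges them related to study procedures.

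**The concern.** Every patient is due one EIT titration with its recruitment phase (Section 5.1.5), first or after crossover, and up to three blind lavages (Sections 5.1.2 and 9). Nearly all consent will come from surrogates (Section 10.2), and Section 9.4 presents the DSMB as part of risk minimization. The board can do that job only if it gets information in time and the information covers the harms it is asked to judge.

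As written, neither is assured. A substantial share of a small trial can be treated before the first scheduled review. The power to halt has no stated source of information between meetings. The mortality data end at a point where few deaths can be expected, particularly as patients not expected to survive 24 hours are excluded (Section 4.3). Beyond that point, a death put down to ARDS by an unblinded investigator need not be recorded at all. Pneumothorax is a listed risk of both mini-BAL and high PEEP (Sections 9.1 and 9.2), and after a late third lavage it can fall outside the collection window.

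**Working it through.** The plan gives no safety event count, detection probability or boundary, so there is no figure of its own to reproduce.

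**1. Patients treated before the first review.** Inputs: 20 patients, accrual of 12 to 24 months (Section 4.1), review every 6 months (Section 11). Assumptions: even accrual, and a first review 6 months after the first enrollment. Number treated = 20 × 6 / accrual months.

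- 12 months: 20 × 6/12 = 10 (50%)
- 18 months: 20 × 6/18 = 6.7 (33%)
- 24 months: 20 × 6/24 = 5 (25%)

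At three lavages each, that is at most 15 to 30 lavages. Some will be withheld under the Section 5.1.2 criteria. Uneven accrual could move the patient count either way.

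**2. Deaths expected in 24 hours.** The documents give no 24-hour mortality, so it has to be assumed. Appendix C quotes 28-day mortality of 49.3% and 55.3% (open-lung recruitment trial) and 60-day mortality of 35% and 46% (ECMO trial). With a constant hazard, q = 1 − (1 − M)^(1/days), expected deaths = 20q, and P(none) = (1 − q)^20.

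| Quoted mortality M | q (24 h) | Expected deaths in 20 | P(none) |
|---|---|---|---|
| 49.3% at 28 days | 2.40% | 0.48 | 0.62 |
| 55.3% at 28 days | 2.83% | 0.57 | 0.56 |
| 35% at 60 days | 0.72% | 0.14 | 0.87 |
| 46% at 60 days | 1.02% | 0.20 | 0.81 |

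If deaths come early, q is higher. Over an assumed range of 1% to 10%, expected deaths in 20 run from 0.2 to 2.0 and P(none) from 0.82 to 0.12. Zero deaths in 20 leaves a one-sided 95% upper limit of 1 − 0.05^(1/20) = 14%.

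**3. The third lavage against the collection window.** In the Appendix F clock example, BAL #1 is at 8:00 and BAL #3, at hour 18 after crossover, is at 9:00 the next day: 25 hours later. It takes about 30 minutes, so it ends at 25.5 hours. Consent and randomization come before BAL #1, so the time since enrollment is longer still. Section 6.3 starts the clock only once PEEP is established, after 20–40 minutes by EIT and 5–10 minutes by table. Adding 25 to 50 minutes for the two settings puts the start at 25.4 to 25.8 hours.

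At the earliest permitted time (hour 14, 5:00) the lavage ends at 5:30. Even with enrollment as late as 8:00, only 2.5 hours of collection remain. Sections 5.1.3 and 5.1.4 end the protocol after the third mini-BAL, whereas Section 11 equates the end of the protocol with 24 hours after enrollment. In the example these are different times.

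**The case against.** The other side has real points.

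- **Silence is not prohibition.** Nothing bars the principal investigator from forwarding an event, and the board may halt at any time. A reader might infer that the board sees nothing for six months, or that its power to halt cannot work. The documents do not support that: they only fail to write the route down. Nor do they say that the first review falls six months after the first patient.
- **Bedside safeguards exist.** Lavage is withheld for low P/F or low platelets and terminated for sustained desaturation, and early termination is reported as an adverse event (Sections 5.1.2 and 9.1). Vital signs are monitored continuously during it. Titration stops for instability or low SpO2 (Section 5.1.5). These protect the individual patient. They do not replace a review of the pattern across patients.
- **The cited harm comes from a different maneuver.** A reader might carry the harm in the open-lung trial over to this one. Section 9.2 attributes it largely to an aggressive, long maneuver that will not be used here. Appendix C gives that maneuver as 60/45, later 50/35, against 40/25 for one minute in Section 5.1.5. Equal risk is not claimed.
- **Late deaths are hard to interpret.** Every patient receives both methods and then returns to the same care, so deaths by day 28 could not be assigned to a PEEP method or separated from background without a comparator. This stands. It limits such data to description, but a board asked to examine mortality is still better served by it than by a count that will probably be zero or one.

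**Conclusion.** The concern holds as a gap in safety oversight, worth closing before enrollment. It does not show that the trial is unsafe.

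Three parts rest on the text alone: no count or event trigger for review, no written route to the DSMB for serious related events, and a 24-hour limit on both deaths and adverse events. The mismatch between the Section 11 window and the Appendix F example is plain arithmetic, and those passages must be reconciled.

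The sizes rest on assumptions. Treating 5 to 10 of 20 patients before the first review requires even accrual and a first review at six months; half the trial is the fast end of that range. The 0.48 to 0.57 expected deaths require a constant hazard and 28-day mortality like that quoted in Appendix C; the 60-day figures imply fewer. The conclusion that 24-hour mortality is thin does not depend on the exact figure: even at an assumed 10% only two deaths would be expected.

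**What to change.** 1. State in Section 11 that every serious procedure-related event is copied to the DSMB when the principal investigator or designee is alerted. Replace the back-reference in Section 9.4 with a list of the data the board receives.
2. Reconcile the Section 11 window with Sections 5.1.3 and 5.1.4 and Appendix F by extending adverse-event collection to cover a stated period after the third mini-BAL. Take all-cause vital status and pneumothorax from the chart to hospital discharge or day 28, as description for DSMB review and not as an efficacy endpoint.
3. Add at least one early DSMB review triggered by patient count, alongside the semi-annual reviews. After the first 5 patients is one example; the exact count is a matter of judgment. It would hold exposure before the first look to 5 of 20 (25%) at any accrual speed, provided that the next enrollment waits for the review.

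The cost is one or two short extra meetings of three in-house reviewers and one chart look-up per patient. The limitation is that late events describe the protocol as a whole and cannot be assigned to either PEEP method.

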## APPENDICES

### A. Exclusion Definitions

#### 1. Child-Pugh Score (Pugh, 1973)

Points	Class
5-6	A
7-9	B
≥ 10	C

[figure not shown]
Measurement	Numerical Score for Increasing Abnormality		
	1	2	3
Ascites	None	Present	Tense
Encephalopathy	None	Grade I or II	Grade III or IV
Bilirubin (mg/dl)	< 2	2-3	> 3
Albumin (g/L)	> 35	28-35	< 28
Prothrombin time (sec. prolonged)	1-4	4-10	> 10

#### 2. Severe Chronic Respiratory Disease

Any of the following is considered severe chronic respiratory disease and excludes a patient from being eligible for enrollment:

- a. FEV1 less than 20 ml/kg PBW (e.g. 1.4 L for a 70 kg person), or
- b. FEV1/VC less than 50% predicted, or
- c. Chronic hypercapnia (PaCO2 greater than 45 mmHg) and/or chronic hypoxemia (PaO2 less than 55 mmHg) on FiO2 = 0.21, or
- d. Radiographic x-ray evidence of any chronic over-inflation or chronic interstitial infiltration, or
- e. Hospitalization within the past six months for respiratory failure in patients with chronic respiratory disease. (PaCO2 greater than 50 mmHg or PaO2 less than 55 mmHg or O2-Sat < 88% on FiO2 = .21).
- f. Chronic restrictive, obstructive, neuromuscular, chest wall or pulmonary vascular disease resulting in severe exercise restriction, e.g., unable to climb stairs or perform household duties, secondary polycythemia, severe pulmonary hypertension (mean PAP greater than 40 mmHg), or ventilator dependency.

[figure not shown]
## B. Flowchart of Management of EIT Study Groups

## C. ARDS Ventilator Management Strategies

### Overview of ARDS Ventilator Management Strategies

University Hospital Respiratory Care  
Michigan Medicine, Ann Arbor MI

FiO 2 /PEEP Tables																	
Lower PEEP/Higher FiO 2 table																	
Step:	1	2	3	4	5	6	7	8	9	10	11	12	13	14	15	16	17
FiO 2	0.3	0.4	0.4	0.5	0.5	0.6	0.7	0.7	0.8	0.9	0.9	1.0	1.0	1.0	1.0	1.0	1.0
PEEP	5	5	8	8	10	10	10	12	14	14	14	16	18	18	18	20	22
Higher PEEP / Lower FiO 2 table (from ROSE study)	1	2	3	4	5	6	7	8	9	10	11	12	13	14	15	16	17
FiO 2	0.3	0.4	0.4	0.4	0.4	0.4	0.4	0.5	0.5	0.5	0.6	0.7	0.8	0.8	0.9	1.0	1.0
PEEP	5	5	8	10	12	14	16	16	18	20	20	20	22	22	22	24	24

Consider Lower PEEP for patients with low PEEP-responsiveness potential (ie, P/F  $\geq$ 150); Higher PEEP if higher PEEP-responsiveness potential (P/F <150) or BMI >35

See page 2 for general comments & recommended reading

Updated: 7/11/18

Pg 1 of 2

## GENERAL COMMENT

Low VT and minimizing Pplat is the only ventilation strategy with a high level of evidence of mortality benefit in ARDS. Therefore, a lung protective ventilation strategy (LPVS) following the ARDS Network strategy (using pressure or volume ventilation) to limit VT (target 6 mL/kg; reduce to 5 or 4 for high Pplat, 7 or 8 for double-triggering) and Pplat ( $\leq$ 30 cm H2O) should be the initial and primary strategy for all ARDS patients.

## E. EIT Studies

### Adult Studies using Dräger Pulmovista EIT to assess PEEP

(as of 7/31/18)

Author, Year	Design	Patients	EIT best PEEP	Other PEEP method(s)	Protocol	EIT Measures	Outcome
Heines, 2018	Observational; describe clinical practice	ARDS (n=39)	Best compromise in OD vs CL (Costa)	Physician preference	- PCV constant IP; - (RM) Incremental PEEP (to 18-20) - Decremental PEEP by 2 cmH2O steps; stop when loss in EELI (derecruitment), RM, decr until EELI loss in dependent area - Do offline analysis	EELI, offline analysis: ODCL-like,	- EIT acquisition feasible in all pts; no complications with trials, - set vs EIT PEEP same (11.7 vs 11.3), but variable individual agreement - 28% of pts was a diff by >4 cm (clin relevant), 38% same - after set to EIT PEEP increased C and P/F (in both <4 and those $\geq 4$ , so RM?)
Karsten, 2017	Observational	Mid to Moderate ARDS (n=15)	Used both ODCL and COV index (i.e., 2 Best EIT)	Cdyn (lowest PEEP associated with highest C)	- VC w/ 7 mL/kg IBW - (RM) Incremental PEEP, starting at 0 to 15 in 5 mbar steps Q4 min, if PIP=40 not reached PEEP increased to 20 and 25. - Decremental PEEP in 2 mbar steps from 15 to 5 Q4 min.	ODCL, COV index	- Best PEEP by COV resulted in lower PEEP than Best PEEP compliance, - Best PEEP per ODCL was higher than based on compliance. - The best compliance did not correspond to PEEP with least overdistension and collapse. (Mean PEEP: BestPEEP COV < BestPEEP compl < BestPEEP ODCL )
Franchineau, 2017	Observational	Severe ARDS on ECMO (n=15)	Best compromise betw CL and OD; CL of $\leq 15\%$ with lowest % OD	N/A	- PC w/ delta-P=14, PEEP 20 (34/20) x20 min - Decremental PEEP from 20 to 0 (if tol), by 5 Q20 min; (no RM pretrial)	ODCL; EELI, delta-impedance	- EIT PEEP was 15, 10 and 5, in 7, 6 and 2 pts respectively; 20 and 0 never selected - High PEEP associated with more OD (50% in some) and lower CL lower PEEP associated with CL ( $>70\%$ in some) - Wide variability of CL and OD among the 5 PEEP levels suggests need for EIT - tidal vol distribution w/decr PEEP trial decreases in medial-dorsal and dorsal and increases in medial ventral and ventral
Eronia, 2017	Observational	ARDS (N=16)	delta EELI (variation)	Lower PEEP table	- Baseline x 20 min: ARDSNet protocol (VC, 6, <30, lower PEEP table, f to pH7.3-7.45, etc.) - RM 40x40, if Delta EELI change >10%, RM 40x40, increase PEEP 2 measure delta EELI again (max PEEP=18) - Also measurements at EIT-PEEP +2	- Regional compliance (Vt%/100% compliance), - Alveolar hyperdistension and collapse, - Amount of recruited volume	- 14 of 16 could get good data; mean 48 min to complete study - EIT-PEEP higher than table-PEEP (13 vs 9) - P/F increased and drive-pressure reduced with EIT-PEEP - calculated that EXPRESS PEEP would be 20.6 vs EIT-PEEP (13.1) - Regional alv OD and CL reduced in dependent and increased in non-dependent
Long, 2015	Observational	ARDS (n=18)	Level to prevent sign CL w/o obvious OD	Baseline PEEP/FiO 2 method not specific, just to SpO 2 >90%	- Baseline (VC w/6 mL/kg (5 or 4 for Pplat), Pplat $\leq$ 30, PEEP/FiO 2 for SpO 2 >90%) x10-15 min - ZEEP: P=0, FiO 2 =1.0, x3-5 min - RM: PEEP to 15 x2 min, if Pplat<40, to 20 x2 min - Decremental: 20 to 5 by 3 Q5-10 min - 2 groups based on RM PaO 2 +PaCO 2 on 100%: Responders(R) >400 vs Non-responders (NR) <400	- % recruited pixels - % OD pixels - GI-TV and GI-FRC	- 18 pts, 10 male, 12 w/pneumonia, - 13 responders (pneumonia in 35 (R) vs 80% (NR), p=0.062) - No diff in ZEEP P/F; PEEP-15: P/F 302 vs 104; PEEP-20: 369 vs 121 - In R: PEEP mainly increased recruitment in dependent and OD in nondependent. PEEP alleviated global inhomogeneity of VT and EELV. - PEEP levels w/o significant CL and OD were identified individually
Blankman, 2014	Observational	Post cardiac surgery (n=12)	PEEP with minimal lung collapse & minimal OD	- Cdyn - P/F	- Ventilated on PC with constant delta-P, I:E, f, FiO 2 throughout study - RM: delta-P=20 while PEEP increased from 5 to 20, by 5 so that 40/20, held for 40 sec - Decremental: delta-P=10 and PEEP=15 x15 min, then drop by 5 to 0 Q10-20 min	- TIV - VSA - COV - GI index - Regional compliance - ITV index (new)	- Cdyn and P/F had highest value at 10 and 15 PEEP - Max values for TIV, regional C and VSA in nonresponders was 5, in responders was 15 - GI index lowest at 10, while COV and RVD index was 15 PEEP - Concluded ITV index was comparable to Cdyn to indicate "best PEEP"
Zhao, 2010	Observational	Periop (n=10)	Lowest GI index	- Cdyn (least sq.); - Intra-tidal compliance-volume curve	- VC (10 mL/kg), f=12, 1:1.5, 100% - Incremental PEEP, 0 to 28 by 2, each for 10 breaths	GI index	- PEEP values for 3 methods: EIT-GI: 12.2; Cdyn:11.4; compliance-volume: 12.2 - Feasible and reasonable to use GI index to select PEEP with respect to ventilation homogeneity

## F. Time-Event Schedule

Clock example	Study hour	Procedures	Vent data	EIT data	HR/ BP	SpO2	ABG	Cytokines	Comments
closest	BL, pre	BL Assess	X		X	X	X		
8:00		BAL#1			X	X		X	BAL procedure time ~30 min
8:30	0	Set PEEP #1	X	X	X	X			Set EIT ~20-40 min vs table ~5-10 min
9:30	1						X	X	ABG 1 H after setting PEEP
10:30	2								
11:30	3								
12:30	4								
13:30	5								
	pre BAL	Assessment	X	X	X	X	X		
14:30	6	BAL #2			X	X		X	BAL procedure time ~30 min
15:00	0	Set PEEP #2	X	X	X	X			
16:00	1					X	X		ABG 1 H after setting PEEP
17:00	2								
18:00	3								
19:00	4								
20:00	5								
21:00	6								
22:00	7								
23:00	8								
0:00	9								
1:00	10								
2:00	11								
3:00	12								
4:00	13								
5:00	14								BAL #3, anytime between hr 14-18
6:00	15								
7:00	16								
8:00	17								
9:00	pre-BAL	Assessment	X	X	X	X	X		
9:00	18	BAL #3			X	X		X	BAL procedure time ~30 min

Data Collected:	Ventilator: mode, set VT, RRset, RRtot, VE, FiO2, PEEP, Ppeak, Pplat, Pmean, PEEPtot,
	vent calcs: drive-P, Cst, Cdyn,
	EIT: delta-EELI, ODCL; COV, GI Index, Regional compliance
	ABG: pH, PaCO2, PaO2, SaO2, BE, HCO3 (if collected for standard of care)
	Cytokines: per protocol

**Definition of Time:** Time 0 is when PEEP is established

Time 6 is 6 hours after PEEP is set

Reset time frames at cross-over

## G. Imputed PaO2/FiO2

SpO 2	FiO 2															
	0.3	0.35	0.4	0.45	0.5	0.55	0.6	0.65	0.7	0.75	0.8	0.85	0.9	0.95	1	
80%	148	127	111	98	89	81	74	68	63	59	55	52	49	47	44	
81%	151	129	113	101	91	82	76	70	65	60	57	53	50	48	45	
82%	155	132	116	103	93	84	77	71	66	62	58	55	52	49	46	
83%	158	136	119	106	95	86	79	73	68	63	59	56	53	50	47	
84%	162	139	122	108	97	89	81	75	70	65	61	57	54	51	49	
85%	167	143	125	111	100	91	83	77	71	67	63	59	56	53	50	
86%	171	147	129	114	103	94	86	79	73	69	64	61	57	54	51	
87%	177	151	132	118	106	96	88	81	76	71	66	62	59	56	53	
88%	182	156	137	121	109	99	91	84	78	73	68	64	61	58	55	
89%	189	162	141	126	113	103	94	87	81	75	71	67	63	60	57	
90%	196	168	147	130	117	107	98	90	84	78	73	69	65	62	59	
91%	203	174	153	136	122	111	102	94	87	81	76	72	68	64	61	
92%	213	182	159	142	128	116	106	98	91	85	80	75	71	67	64	
93%	223	191	168	149	134	122	112	103	96	89	84	79	74	71	67	
94%	236	202	177	157	142	129	118	109	101	94	89	83	79	75	71	
95%	252	216	189	168	151	138	126	116	108	101	95	89	84	80	76	
96%	273	234	205	182	164	149	136	126	117	109	102	96	91	86	82	

The table is used when an ABG is not available to calculate the PaO2/FiO2. Instead, the SpO2 and FiO2 are used to impute what the PaO2/FiO2 might be. The following conditions must be met:

1. SpO2 between 80-96%
2. SpO2 should be measured at least 10 minutes after any FiO2 change
3. PEEP must be  $\geq 8$  cm H2O
4. An adequate pulse oximetry waveform tracing is present

